6.7 Identification of participants and treatment assignment

Potentially eligible patients will be identified through the “post MI LVSD” or general cardiology out-patient clinics throughout NHS Greater Glasgow and Clyde (NHS GG&C) and surrounding health boards. Participants will be identified from electronic searching of the cardiac patient databases by a clinical research fellow, who is a member of the direct clinical care team. They will also be identified by clinicians and nurses responsible for the routine care of these patients, for example cardiac rehabilitation nurses, cardiology pharmacists and cardiologists.

Patients will be considered if they have suffered a myocardial infarction at least 3 months prior to randomisation.

The definition of myocardial infarction will be in line with the guidelines provided by the European Society of Cardiology and the third Universal definition of myocardial infarction.^{34,35} Patients will require to meet the following criteria:

- Detection of rise and/or fall of cardiac biomarker values (preferably troponin) with at least one value above the 99th percentile of the upper reference limit and with at least one of the following:
 - Symptoms of ischaemia;
 - New or presumably new significant ST-T changes or new LBBB;
 - Development of pathological Q waves in the ECG;
 - Imaging evidence of new loss of viable myocardium, or new regional wall motion abnormality;
 - Identification of an intracoronary thrombus by angiography or autopsy.

Assenting patients who meet the eligibility criteria and without any contraindications to taking part in the study will be given information regarding the trial as detailed in the patient information sheet. If agreeable to taking part in the trial, then written, informed consent for will be sought. Enrolled patients will be allocated a unique patient identifier number which will last for the duration of the entire trial. The assessment of eligibility and the informed consent process will be undertaken by a member of the research team who is qualified by training and experience in taking informed consent to good clinical practice (GCP) standards. Informed, written consent is necessary prior to randomisation. A copy of the consent form will be given to the patient and another will be uploaded to the patient's online case notes. The original consent form will be filed in the study file and sites will be required to scan and upload the consent forms into a secure study database for each consented patient.

After all baseline data has been collected and the patient has been confirmed as eligible for randomisation, the patient will be randomised via the study web portal. Randomisation will be stratified on the basis of LVESVI $\leq 45\text{ml/m}^2$ / $>45\text{ml/m}^2$ as measured by CMR, and whether or not the patient is being prescribed diuretics at baseline. The portal will inform the researcher of the treatment packs to be allocated to the patient. Randomisation may occur up to three months after screening echocardiography.

6.8 Monitoring of potential side effects

6.8.1 Management of nephrotoxicity

Both study drugs are potentially nephrotoxic and close monitoring of renal function (serum urea, creatinine and electrolytes) for the duration of the trial will be mandatory. This will include baseline measurements along with measurements prior to and after the introduction of the study drug and after any dose change. Measurements will also be taken at regular intervals for the duration of the trial. Alert ranges for laboratory and other test abnormalities are included in Appendix 1. Additional measurements will be used if clinically indicated. All results will be reviewed in a timely manner when available and if action is required this will be expedited immediately. Each patient will have their renal function (along liver function tests) checked at the following time-points:

- Visit 1: Week 0 (pre-randomisation)
- Visit 2: Week 1 (± 3 days)
- Visit 3: Week 2 (± 3 days)
- Visit 4: Week 4 (± 3 days - pre up-titration of study drug)
- Visit 5: Week 5 (± 3 days - 1 week post up-titration of study drug)
- Visit 6: Week 14 (± 7 days)
- Visit 7: Week 26 (± 7 days)
- Visit 8: Week 39 (± 7 days)
- Visit 9: Week 52 (± 7 days)

If, at any time after randomisation, eGFR decreases by $\geq 25\%$ from baseline (or if serum creatinine concentration increases to $221\text{ }\mu\text{mol/L}$), potentially reversible cases of renal dysfunction will be sought including: non-steroidal anti-inflammatory drug

intake, antibiotics, or other nephrotoxic medications; hypovolaemia; and urinary tract infection. If felt to be appropriate, the study drug dose can be reduced and continued with regular monitoring of renal function. If a patient's eGFR decreases by $\geq 40\%$ from baseline (or if serum creatinine concentration rises above 265 $\mu\text{mol/L}$, then this is an indication to stop the study drug. Thereafter, serum creatinine assessments will have to be repeated at least weekly until levels return to acceptable values. Re-challenging with the study drug at a lower dose level will be considered if deemed clinically safe to do so.

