A dose level 1 (sacubitril/valsartan 24mg/26mg B.D) will be available during the double-blind period of the trial should patients require down-titration but the aim is to maintain the patient on the target dose level 3 for as long a duration as possible during the trial. (*Figure 4-1 Study drug initiation and up-titration*) This dose can be also be considered at the time of randomisation with a two-step titration to target dose over visits 3 and 4 if systolic BP at visit 1 is ≥ 100 to 110mmHg. Additionally, dose level 1 should be considered as initial dose in patients with moderate renal impairment (eGFR 30-60 ml/min/1.73 m²).

Table 4-2 Study drug dose levels during treatment period

Dose Level	Sacubitril/Valsartan arm	Valsartan arm
1	24mg/26mg B.D.	40mg B.D.
2	49mg/51mg B.D.	80mg B.D.
3	97mg/103mg B.D.	160mg B.D.

Figure 4-1 Study drug initiation and up-titration

* Equivalent doses detailed in *Table 4-1*

Dose level 1 can be considered for patients with SBP ≥ 100 to 110mmHg and/or moderate renal impairment (eGFR 30-60 ml/min/1.73 m²) at time of randomisation

+ down titration from dose level 3 to dose level 2 permitted during extension of treatment times in response to COVID-19 pandemic

Following randomisation the aim should be to up-titrate patients to target study drug dose level 3 (*Table 4-2*) after 4 weeks (Visit 4). Slower up-titration will be permitted if necessary to ensure patient safety and tolerability. Patients will be allowed to stay at dose level 1 or 2 as maintenance dose however efforts should be made to maintain patients on the target dose level 3 or maximally tolerated dose level for as long a duration as possible during the trial. Adjustments to study drug dose level should be based on safety and tolerability with a focus on a) symptomatic hypotension, b) clinically significant decline in renal function and c) hyperkalaemia (*Table 4.3*).

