6.1 Investigational and control drugs

All eligible patients will be randomised 1:1 to either sacubitril/valsartan titrated to a target dose of 97mg/103mg B.D. or valsartan titrated to a target dose of 160mg BD in a double blinded manner for the duration of the study. Patients will continue on optimal standard of care background therapy to treat their index MI and any co-morbid conditions in accordance with local guidelines with the exception of an ACE inhibitor or ARB as this will be replaced by study drug. In order to minimise the potential risk of angioedema due to overlapping ACE and NEP inhibition all patients prescribed an ACE inhibitor pre-randomisation will undergo a 36-hour “washout” period following randomisation prior to first dose of study drug. The use of open label ACE inhibitor or ARB in addition to the randomised study drug is strictly prohibited for the duration of the trial.

In order for adequate blinding of treatment allocation, patients will be required to take a total of two tablets (one tablet from the sacubitril/valsartan or sacubitril/valsartan matching placebo pack and one tablet from the valsartan or valsartan matching placebo pack) twice a day for the duration of the study.

The following study drugs will be provided:

- Sacubitril/valsartan 24mg/26mg, 49mg/51mg and 97mg/103mg tablets and matching placebo.
- Valsartan 40mg, 80mg and 160mg tablets and matching placebo.

Patients will be supplied with sufficient medication to last to the next visit including a small overage at visits 1, 4, 6 and 7. At each study visit where medicines are dispensed, patients will be asked to return any unused study drug and this will be returned to the pharmacy. In response to the COVID-19 pandemic re supply in person at the CRF or through home delivery at unscheduled intervals until the final MRI is performed (up to a maximum of 18 months or end of study).

Patients will be advised to take their morning study drug doses at approximately 08:00 (8 AM) and their evening dose 12 hours later at approximately 20:00 (8PM). The study medicines should be swallowed whole with water and can be taken with or without food. If a patient misses a dose of either study drug they should skip the missed dose and take the next one at the scheduled time.

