8.2.2 CMR protocol

All CMR scans will be performed on a single 3.0 Tesla Siemens MAGNETOM Prisma scanner located in the CRF at the QEUH. The MRI scan will include cine MRI, T1 and T2 maps, strain encoded MRI, and contrast enhanced imaging including first pass perfusion at rest, microvascular obstruction and late gadolinium enhancement imaging 10 - 15 min after contrast administration. IV access will be required for contrast administration and a full blood count will be obtained before the scan in order to measure extracellular volume. Specific details of the CMR protocol are detailed in a local Standard Operating Procedure. Patients will be provided with an MRI information sheet prior to their visit (Appendix 2).

8.3 26-week visit

This will comprise of a half-day visit to the QEUH CRF. A number of the baseline investigations will be repeated:

- full physical examination
- spot urine collection
- venepuncture – 50ml blood withdrawn for biochemical and hormonal analysis

Patients will also be asked to complete a short patient global assessment questionnaire (Appendix 3) at this visit.

8.4 52-week visit (+/- 3 months)

This will comprise of a half-day visit to the QEUH CRF. A number of the baseline investigations will be repeated:

- full physical examination
- spot urine collection
- venepuncture – 50ml blood withdrawn for biochemical and hormonal analysis
- cardiac MRI with gadolinium contrast will be performed.

Patients will also be asked to complete a short patient global assessment (Appendix 3) questionnaire at this visit.

In response to the COVID-19 pandemic we have allowed an extension of the patients IMP treatment by up to 3 months. During this extended time on IMP we would anticipate following up with patients by telephone every 6 weeks. Patients have the clinical research team contact details should they wish to discuss any aspect of the extended involvement themselves.

At this point a patient's participation in the involvement in the trial will end. They will return any unused study drug. Following their involvement in the trial patients will be converted to an ACE-inhibitor or ARB as per local practice guidelines at an equivalent dose to their final study drug dose level. Prior to commencement of any ACE-inhibitor, patients will require to have a 36-hour washout period following their last dose of study drug in order to reduce the risk of angioedema associated with combined ACE and NEP inhibition.

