8.5 Definition of end of trial

The end of the trial is defined as the date of the last patient's 52-week (+/- 3 months) study visit plus additional 30 days of event reporting.

9 Assessment, samples and data collection

Trial data will be recorded on trial-specific eCRFs. Only the patient's unique identifier number, date of birth and initials will be recorded on the eCRF in order to identify the patient. Any missing or discrepant data queries will be sent to appropriate research

team member(s) to be reviewed. Biochemical samples will be stored in the QUEH Biochemistry department and the BHF Glasgow Cardiovascular Research Centre to be analysed in batches on completion of the trial. Analysis of echocardiograms and CMR imaging will be performed offline.

Table 9-1 Schedule of Assessments

Study Procedure	Screening (>3months post myocardial infarction)	Visit 1 - Randomisation (Week 0)	Visit 2 (Week 1 ± 3 days)	Visit 3 (Week 2± 3 days)	Visit 4 (Week 4± 3 days)	Visit 5 (Week 5± 3 days)	Visit 6 (Week 14 ± 7 days)	Visit 7 (Week 26 ± 7 days)	Visit 8 (Week 39 ± 7 days)	Visit 9 (Week 52 ± 3 months)
Review Inclusion/Exclusion Criteria	X									
Echocardiogram	X									
Obtain informed consent	X	X								
Cardiac MRI		X								X
Physical examination		X	X		X			X		X
Medical history	X	X								
Concomitant medications	X	X	X	X	X	X	X	X	X	X
Vital Signs (Blood pressure/Heart rate)	X	X	X	X	X	X	X	X	X	X
12 Lead ECG		X								
Spot urine collection		X						X		X
Venepuncture (Urea and Electrolytes/FBC and LFTs)	X&	X	X	X	X	X	X	X	X	X
Venepuncture (Biochemical/hormonal/biomarker analysis)		X						X		X
Pregnancy testing in WoCBP		X			X		X	X	X	X
Patient global assessment questionnaire								X		X
IMP Dispensing*		X			X		X	X		
Up-titrate IMP#					X					
IMP Administration+		X	X	X	X	X	X	X	X	X
Adverse event reporting			X	X	X	X	X	X	X	X
Study completion										X

* Study drug will be introduced at equivalent dose to existing ACE-i/ARB treatment (Dose level 2 or 3) at investigator's discretion

#Up-titration not required if patient already on dose level 3 but down titration to dose level 2 permitted in response to COVID-19

&If not done in the preceding 6 months

+Emergency IMP dispensing permitted during COVID-19 pandemic

10 Pharmacovigilance

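### The protocol does not say whether the mandatory Week 52 renal bloods move with the delayed Visit 9; if they do, up to 26 weeks on study drug can pass without a scheduled U&E, against 13 nominal

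*Protocol*

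**What the plan says.** Protocol 6.8.1 states that "close monitoring of renal function (serum urea, creatinine and electrolytes) for the duration of the trial will be mandatory". It asks for "measurements prior to and after the introduction of the study drug and after any dose change", for measurements at regular intervals, and for extra ones when clinically indicated. It then lists nine fixed time-points. The last two are Visit 8 at Week 39 ± 7 days and "Visit 9: Week 52 (± 7 days").

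The COVID-19 changes moved the same visit elsewhere in the protocol. In Table 9-1 the column reads "Visit 9 (Week 52 ± 3 months"). Section 8.4 says "we have allowed an extension of the patients IMP treatment by up to 3 months" and then "During this extended time on IMP we would anticipate following up with patients by telephone every 6 weeks". Table 9-1 has a U&E at Visit 8 and at Visit 9 and no column between them. Section 4.1 ties U&Es to study visits.

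Study drug continues in the meantime. Section 6.1 allows resupply in person at the research facility or "through home delivery at unscheduled intervals until the final MRI is performed (up to a maximum of 18 months or end of study"). A footnote to Figure 4-1 in section 4.1 has "down titration from dose level 3 to dose level 2 permitted during extension of treatment times in response to COVID-19 pandemic".

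Section 8 asks that visit windows be met wherever possible, does not treat visits outside them as protocol violations, and leaves their handling to the SAP. The SAP deals with late MRI scans (2.4.1 and 2.4.4) but says nothing about late safety bloods.

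**The concern.** The Visit 9 window was widened in 8.4 and Table 9-1 but not in 6.8.1. Site staff therefore have two rules for one safety sample: due by Week 53, or acceptable as late as Week 65. A site that follows Table 9-1 will draw the blood when the patient comes for the scan.

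The action rules need a laboratory result. Section 6.8.1 acts on eGFR falls of at least 25% or 40%. Section 6.8.2 acts on potassium above 5.3, above 5.5, or at 6.0 mmol/L and over. A telephone call cannot supply these values, and a silent rise in potassium gives no reason to order a test. Patients may enter with eGFR as low as 30 and potassium up to 5.2 mmol/L (section 5.2), so some start near a threshold.

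There is a smaller reporting consequence. SAP 2.5.2 counts worsening renal function or acute kidney injury, and hyperkalaemia. If the sample moves with the visit, an extended patient adds up to 13 weeks on drug with one scheduled laboratory look at the end. An event that arises and resolves in that time may not be recorded.

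**Working it through.** The documents give no figure for this interval, so there is none of the plan's own to reproduce. The check is calendar arithmetic, in weeks from randomisation.

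**Inputs**
- Visit 7: Week 26 ± 1; Visit 8: Week 39 ± 1 (6.8.1, Table 9-1).
- Visit 9 under 6.8.1: Week 52 ± 1.
- Visit 9 under 8.4 and Table 9-1: Week 52 ± 3 months. Three months = 3 × 365.25 / 12 / 7 = 13.04 weeks, taken as 13, so the latest is Week 52 + 13 = 65.
- Planned contact in the extension: telephone every 6 weeks (8.4).

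**Schedule in 6.8.1.** Visits at Weeks 0, 1, 2, 4, 5, 14, 26, 39 and 52 give successive gaps of 1, 1, 2, 1, 9, 12, 13 and 13 weeks. The longest nominal gap is 13.

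**Interval from Visit 8 to the next scheduled U&E**

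| Rule for the sample | Nominal | Shortest | Longest |
|---|---|---|---|
| 6.8.1: Week 52 ± 1 | 52 − 39 = 13 | 51 − 40 = 11 | 53 − 38 = 15 |
| Moves with Visit 9, at its latest (Week 65) | 65 − 39 = 26 | 65 − 40 = 25 | 65 − 38 = 27 |

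The Visit 7 to Visit 8 gap can also reach 40 − 25 = 15 weeks, so 15 is the longest interval that 6.8.1 allows anywhere. The late limit adds 26 − 13 = 13 weeks and doubles the nominal spacing.

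**What falls inside the extension.** Counting from Week 52, six-weekly calls come at Weeks 58 and 64. That is two calls and no scheduled sample before Visit 9 at Week 65.

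**Effect of keeping a sample near Week 52.** With a window of ± w weeks, the longest gap before the sample is (52 + w) − 38 = 14 + w, and the longest gap from it to Week 65 is 65 − (52 − w) = 13 + w. With w = 1 these are 15 and 14 weeks, so no interval exceeds the 15 already allowed. Each further week of window adds one week.

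**The case against.** The strongest reply is that 6.8.1 stands as written. Its list is introduced as mandatory, it still gives Week 52 ± 7 days, and silence in 8.4 cancels nothing. On that reading the gap stays at 13 weeks, 15 at most, and only a window needs tidying. This is a fair reading, and it rules out saying flatly that no U&E is scheduled for 26 weeks. It does not settle the matter, because 6.8.1 attaches those bloods to Visit 9, and Visit 9 is what moved.

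Other parts of the reply also stand. Thirteen of the 26 weeks were always planned. Bloods after a dose change, or if clinically indicated, still apply in the extension. Most patients will be on a settled dose by then, and the dose change expressly allowed for COVID-19 is downward. Transient laboratory events can be missed at 13-week spacing too. The wide window was a pandemic measure, so asking for attendance at Week 52 carries an access burden.

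A reader might infer three stronger things that the documents do not support:
- *Contact in the extension is by telephone only.* Section 8.4 says telephone follow-up is anticipated, and 6.1 also offers in-person resupply. What is missing is a sample attached to either.
- *The reduce and stop rules cannot operate.* Section 6.8.1 applies its renal thresholds at any time after randomisation, so a result from an unscheduled test triggers them.
- *The gap could reach about 39 weeks because 6.1 mentions 18 months.* That limit concerns drug supply. The synopsis and section 4.1 set treatment at 12 ± 3 months, and 8.4 allows at most 3 extra months, so treatment ends by 15 months.

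**Conclusion.** The point holds as an unresolved conflict in the current protocol text, with a patient-safety consequence. If the renal sample travels with the delayed Visit 9, a patient can be on study drug for up to 26 weeks (25 to 27) without a scheduled U&E, against 13 nominal and 15 at most under 6.8.1.

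This assumes 3 months = 13 weeks, Visit 9 at its latest permitted date, and a site that follows 8.4 and Table 9-1 instead of the list in 6.8.1. It is a maximum for extended patients, not a typical value, and the documents do not say how many patients were extended.

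A reader might go on to infer bias in the safety comparison or the trial result. The documents do not support that: the schedule is the same in both blinded arms, and the primary endpoint does not depend on U&Es. The change is worth making because it is cheap and restores a check that 6.8.1 already lists.

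**What to change.** 1. In 6.8.1 and Table 9-1, separate the renal safety sample from the MRI visit. Keep one U&E at about Week 52 for every patient still on study drug, drawn at in-person resupply, at the GP or in routine care. Use ± 7 days where feasible and a stated wider window where pandemic access requires it. List Visit 9 itself as Week 52 ± 3 months in both places.
2. Align the 18-month supply limit in 6.1 with the 15-month maximum treatment (12 + 3) in 4.1 and 8.4.

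**Cost.** One blood draw per extended patient, which 6.8.1 already lists, plus some access burden during the pandemic. The number extended is not given; if 10%, 25% or 50% of the 100 patients were extended, that is 10, 25 or 50 samples. Section 4.1 already accepts routine-care U&Es within 14 days of a visit for up-titration decisions, so the route has a precedent. Sample size, blinding and endpoints are unaffected.

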6.8.2 Management of hyperkalaemia

Patients with elevated potassium value will be managed according to the corrective actions outlined below.

Serum potassium > 5.3 and less than or equal to 5.5 mmol/L

- Confirm potassium concentration in a non-haemolysed sample
- Reinforce low potassium diet and restriction of food/drinks with high potassium content
 - (e.g. orange juice, melon, bananas, low-salt substitutes etc.)
- Review medical regimen (including dietary supplements and over-the-counter medications) for agents known to cause hyperkalaemia. Consider reduction in dose or discontinuation of these agents:
 - Potassium-sparing diuretics (e.g. amiloride and triamterene) including in combination products with thiazide or loop diuretics
 - Potassium supplements, e.g., potassium chloride
 - Salt substitutes
 - Non-steroidal anti-inflammatory drugs (NSAIDs)
 - Cyclo-oxygenase-2 (COX-2) inhibitors
 - Trimethoprim and trimethoprim-containing combination products
 - Herbal Supplements: For example, Noni juice, alfalfa (*Medicago sativa*), dandelion (*Taraxacum officinale*), horsetail (*Equisetum arvense*), nettle (*Urtica dioica*), milkweed, lily of the valley, Siberian ginseng, hawthorn berries
- Repeat serum potassium measurement within 3 to 5 days
- If serum potassium remains > 5.3 and ≤ 5.5 mmol/L, regularly monitor serum potassium levels to ensure stability (suggested once monthly)
- Consider down-titration of study medication, according to investigator's medical judgment.

Serum potassium > 5.5 and < 6.0 mmol/L

- Confirm potassium concentration in a non-haemolysed sample
- Consider down-titration or temporarily discontinue study drug according to investigator medical judgment.
- Apply all measures outlined for serum potassium > 5.3 and ≤ 5.5 mmol/L
- Repeat serum potassium measurement after 2-3 days
- If serum potassium < 5.5 mmol/L, consider resumption of study drug at lower dose with repeat potassium within 5 days

Serum potassium greater than or equal to 6.0 mmol/L

- Immediately discontinue study drug

- Confirm potassium concentration in a non-haemolysed sample
- Urgently evaluate patient and treat hyperkalaemia as clinically indicated
- Apply all measures outlined for serum potassium > 5.3 and < 6.0 mmol/L
- Resumption of study drug will be decided on a case-by-case basis by the investigators.

